5.7. Screen Failures

Screen failures are defined as participants who consent to participate in the clinical study but are not subsequently included in the study. A minimal set of screen failure information is required to ensure transparent reporting of screen failure participants to meet the Consolidated Standards of Reporting Trials (CONSORT) publishing requirements and to respond to queries from regulatory authorities. Minimal information includes demography, screen failure details, eligibility criteria, and any serious adverse events (SAE).

Individuals who do not meet the criteria for participation in this study (screen failure) may be rescreened. Rescreened participants will be assigned the same participant number as for the initial screening.

6. Treatments

Study treatment is defined as psychiatric treatment within either Outpatient Crisis Intervention Clinic (OCIC), on an Inpatient unit, or telehealth crisis intervention services. Participants will be placed in the treatment setting by the assessing clinician. These therapeutic interventions are available whether or not the subject agrees to participate in the study.

Telehealth crisis intervention services (telehealth CIS) is defined as psychiatric services provided via telehealth services that is expected to be scheduled within 7 business days of the crisis assessment. Interventions can be with a social worker, therapist or psychiatrist. Services are not in person and occur over a computer video/phone system.

Inpatient treatment includes supportive individual therapy, improving patient's coping skills, family meetings about safety planning, and medication management.^{6-9, 81}

OCIC services include crisis psychotherapy/intervention, evidence-based screening/risk assessments, coordination of care/referral to an ongoing provider, short-term therapy/crisis treatment, safety planning, and/or referral and linkage to follow-up care. Treatment in OCIC may include group therapy, individual therapy, and/or family therapy, depending on the site. Please

see below for full description of services by site. Adolescents in OCIC will be referred to a psychiatrist for medication management as needed. OCIC provides crisis intervention therapy and/or components of Cognitive Behavior (CBT), Dialectical Behavior Therapy (DBT), mindfulness CBT, Relapse Prevention CBT, and/or Supportive Psychotherapy. The length of time in OCIC and telehealth CIS can range from around one to six weeks depending on the needs of the patients and families. Due to the pragmatic approach to the research design, interventions provided will be site specific but all sites will include the crisis intervention component, including crisis stabilization (therapeutic intervention) and safety planning and assessment. Additionally, patients will have the expectation of being scheduled to be seen within 7 business days of the ED visit for follow up care. The charts below outline a description of the OCIC program, Inpatient services, and Telehealth CIS services provided at each of the four sites.⁴⁰⁴³ The following is an explanation of services provided in the treatment arms. All treatment is clinically based and data will be collected. No decisions on treatment will be part of this study and the data from this study will not be shared with clinicians to alter care.

Site	Describe intervention with patient	Describe intervention with family	Length of visit	Length of treatment	Staff performing treatment	Plan if subject has increased risk of suicide
Cincinnati	
A crisis intervention appointment will entail:
 
 1. Identification of current crisis and precipitants 2. Exploration of feelings/emotions using components of CBT, DBT and other therapies 3. Identification and exploration of coping skills and resources 4. Safety planning and assessment 	
1. Family support 2. Safety assessment and planning 3. Referral to psychiatric provider for evaluation for need of medication 4. Referral and connection to outpatient provider for continued care.
	60 min or longer as needed	Average 1-3 sessions, longer as needed	Licensed Independent Social workers, Clinical Counselors, APRNs and child and adolescent psychiatrist for medication management	Pt would be referred to the ED for evaluation or admitted to inpatient by clinical staff.

Site	Describe intervention with patient	Describe intervention with family	Length of visit	Length of treatment	Staff performing treatment	Plan if subject has increased risk of suicide
New York	
A crisis intervention appointment will entail:
 
 1. Identification of current crisis and precipitants 2. Exploration of feelings/emotions using components of CBT and other therapies 3. Identification and exploration of coping skills and resources 4. Safety planning and assessment 	
1. Family support and psychoeducation
 
2. Safety assessment and planning
 
3. Psychopharmacology
 
4. Referral and connection to outpatient provider for continued care.
	60 min or longer as needed	Average 1-3 sessions, longer as needed	Licensed Independent Social workers, Clinical Counselors, APRNs and child and adolescent psychiatrist and fellows under supervision for medication management	Pt would be referred to the ED for evaluation or admitted to inpatient by clinical staff.

Site	Describe intervention with patient	Describe intervention with family	Length of visit	Length of treatment	Staff performing treatment	Plan if subject has increased risk of suicide
Columbus	
A crisis intervention appointment will entail:
 
 1. Identification of current crisis and precipitants 	
1. Family support
 
2. Safety assessment and planning
 
3. Referral to psychiatric provider for evaluation
	60 min or longer as needed	Average 1-3 sessions, longer as needed	Licensed Independent Social workers, Clinical Counselors, APRNs and child and adolescent	Pt would be referred to the ED for evaluation or admitted to inpatient by clinical staff.

	
2.Exploration of feelings/emotions using components of CBT, DBT and other therapies
 
3.Identification and exploration of coping skills and resources
 
4.Safety planning and assessment
	for need of medication 4. Referral and connection to outpatient provider for continued care.			psychiatrist for medication management	
--	---	---	--	--	--	--

Site	Describe intervention with patient	Describe intervention with family	Length of visit	Length of treatment	Staff performing treatment	Plan if subject has increased risk of suicide
Dallas	
A crisis intervention appointment will entail:
 
1.Identification of current crisis and precipitants
 
2.Exploration of feelings/emotions using components of CBT, DBT and other therapies
 
3.Identification and exploration of coping
	
1.Family support (on an individual level)
 
2.Safety assessment and planning
 
3. Multi-family group, which includes family wellness, communication, strength building
 
4. Referral and connection to outpatient provider for continued care.
	
Group (9 hrs/week, which includes two teen groups and one multi-family group), Once weekly individual therapy (60 minutes)
	
Treatment duration is 4-6 weeks, Follow-up assessment phone calls at 1 month and 6 months post-discharge
	
Licensed Clinical Social workers, Licensed Professional Counselors, and child and adolescent psychiatrists for medication management; All of the above include trainees performing treatments under the supervision of licensed providers
	
First preference is direct admission to Inpatient Unit (either at our site or in the community); if after hours, refer patient to ED

	
skills and resources
 
4. Safety planning and assessment
 
5. Psychiatric evaluation and medication management, as needed
 
*Note: #2 and #3 above are done in both individual and group format throughout the course of treatment
					
--	--	--	--	--	--	--

Treatment Components

Inpatient

	Medication evaluation and management	Safety planning	Individual and family therapy	Skills groups	DBT program with skills group	Length of stay
Dallas	X	X	X	X		7 days
New York	X	X	X		X	8 days
Nationwide Children's	X	X	X	X		8 days
Cincinnati	X	X	X	X		6 or 7 days

Outpatient (OCIC)

	Group therapy	Individual and family therapy	Referral to psychiatrist for med management	Crisis stabilization/safety reassessment	Safety Planning	Parents attend skills class	Length of treatment
Dallas	X	X	X	X	X	X	4-6 weeks
New York		X	X	X	X		3 visits
Nationwide Children's		X	X	X	X		1-6 weeks
Cincinnati		X	X	X	X		1-6 weeks

Telehealth Crisis Intervention Services CIS

	Individual and family therapy	Referral to psychiatrist for med management	Crisis stabilization/safety reassessment	Safety Planning	Length of treatment
Dallas	X	X	X	X	4-6 weeks
New York	X	X	X	X	1-3 visits
Nationwide Children's	X	X	X	X	1-6 weeks
Cincinnati	X	X	X	X	1-6 weeks

Once a patient has agreed to participate in the study, meets eligibility, and has given consent/assent, they will be followed in their treatment group. The patient's treatment will be done by social workers, doctors (MD), and/or other mental health professionals.

6.1. Method of Treatment Assignment

All eligible individuals will be followed in three treatment arms: OCIC versus inpatient treatment versus telehealth groups. Potential participants will be identified once they have been assigned to a treatment setting by a licensed clinician at each institution (Cincinnati, Dallas, Columbus, and New York). Research coordinators will be in contact with clinicians who complete the assessments to identify appropriate participants. The CHRT-SR will be reviewed to identify participants who meet study criteria (i.e. need higher level of treatment due to suicidal thoughts). Once a potential participant is identified, research coordinators will contact guardians via phone to introduce the study and complete remote enrollment and consenting procedures.

6.2. Treatment Compliance

For this study, treatment compliance is defined as adhering to appointments assigned by assessing clinician to telehealth or OCIC and not leaving against medical advice (AMA) if assigned to inpatient treatment. For patients who are not treatment compliant, attempts will be

made by the study staff to follow up and encourage recommended treatment. Study staff will work with PIRC or equivalent to complete up to two phone calls or text messages to attempt to contact patients who do not show for scheduled telehealth appointments, OCIC appointments, or inpatient recommendation. If we are unable to contact these patients or they refuse any or all follow up treatment (including telehealth, OCIC, inpatient or outpatient recommendations), we will continue to follow them until they withdraw from the study. If patients refuse telehealth, OCIC or inpatient treatment from the emergency department or crisis assessment, we will continue to follow these patients until they withdraw from the study. For patients who are AMA from the inpatient unit, this process of following up regarding services will be addressed by the inpatient treatment team. It is standard of care for inpatient treatment teams to not provide prescriptions and follow up services for AMA's but this practice varies based on the inpatient treatment team. If the AMA (from inpatient treatment) patient remains in our study, we will encourage the AMA patient to return to treatment (inpatient, OCIC, and/or telehealth outpatient).

6.3. Treatment After the End of the Study

Follow up care after the end of this study will be decided by the participants' parents'/guardians', therapist, mental health professional, and/or physician.

7. Discontinuation Criteria

It is unlikely that a patient will be discontinued from the study during the inpatient, telehealth, or OCIC phase of the study. If patient experiences worsening symptoms while inpatient, this treatment will be extended to meet their needs as identified by inpatient clinicians. Patient in the OCIC or telehealth treatment arms with worsening symptoms may be recommended for evaluation in the ED, referral for inpatient, and/or connected to outpatient services as identified by a qualified mental health clinician. If a patient is involved in an adverse event that is associated with study procedures, leading to harm, the DSMB and external medical monitor may identify the need for removal from the study for safety concerns. This is unlikely but will be monitored by the DSMB, EMM and IRB

7.1. Discontinuation from the Study

- A participant may withdraw from the study at any time at his/her own request, or may be withdrawn at any time at the discretion of the investigator for safety, behavioral, or administrative reasons.
- If the participant withdraws consent for disclosure of future information, the sponsor may retain and continue to use any data collected before such a withdrawal of consent.
- Refer to the Schedule of Events (SoE) in the Appendix for data to be collected at the time of study discontinuation and follow-up and for any further evaluations that need to be completed.

7.2. Lost to Follow Up

A participant will be considered lost to follow-up if he or she repeatedly fails to complete surveys and/or fails to return for scheduled visits and is unable to be contacted by the study site.

The following actions must be taken if a participant fails to return to the clinic for a required study visit or fails to complete the surveys/questions that occur about every 2 weeks:

- The site must attempt to contact the participant and reschedule the missed survey or visit as soon as possible and counsel the participant on the importance of maintaining the assigned survey or visit schedule and ascertain whether or not the participant wishes to and/or should continue in the study. Text messaging may be used as a method of communication with the participant to encourage survey completion and/or to notify that further communication by phone or in person is needed.
- In cases in which the participant is deemed lost to follow up, the investigator or designee must make every effort to regain contact with the participant (where possible, 3 telephone calls and, if necessary, a certified letter to the participant's last known mailing address or local equivalent methods). These contact attempts should be documented in the participant's research record.

- Should the participant continue to be unreachable, he/she will be considered to have withdrawn from the study with a primary reason of lost to follow-up.

8. Study Assessments and Procedures

- Study procedures and their timing are summarized in the SoE (Appendix). Surveys are administered and requested for completion every 2 weeks. Data will be collected upon return of surveys. If surveys are not completed within 10 days of milestone window, that window will be skipped and study team will request data at the next milestone window.
- Baseline data and follow surveys/forms will be completed through REDCap and/or paper forms. CCHMC REDCap can collect almost any type of data, and is particularly designed to support online and offline data capture for research studies and operations.
- Adherence to the study design requirements, including those specified in the SoE, is essential and required for study conduct.
- All screening evaluations must be completed and reviewed to confirm that potential participants meet all eligibility criteria. The investigator will maintain a screening log to record details of all participants screened and to confirm eligibility or record reasons for screening failure, as applicable.
- Time to first recurrence of a suicidal event and number of suicidal events will be measured with the Suicidal Event Form for START (appendix), a short supplemental form (developed by our team), at baseline and every two weeks (see Schedule of Events; appendix)
- Severity of suicidal ideation will be measured with the self-report scale: CHRT-SR (appendix) at baseline and every two weeks (see Schedule of Events; appendix).
- The Suicidal Treatment AlteRnatives for Teens (START)-Clinical Features (CF) form (appendix), a short supplemental form with 13 questions (developed by our team), will be completed at baseline (within 72 hours of admission to inpatient or OCIC) and every two weeks to monitor substance use based on information from patient, parent, and/or EHR.
- The C-SSRS Self-Report form, included in the CF survey, will be completed at baseline and every 2 weeks by the participant to assess for suicidal thoughts and behaviors.
- Satisfaction with Life (SL) will be measured with self-report scales including the PROMIS Short Form v 1.0-General Life Satisfaction-Short Form 5a (to assess the parent's well-being), PROMIS Parent-Proxy Life Satisfaction-Short Form 8a, and PROMIS Pediatric Life Satisfaction-Short Form 4a every 2 weeks.
- Treatment satisfaction (TS) data about, telehealth CIS, OCIC and inpatient psychiatry will be collected only after two weeks and/or subsequent to completion of inpatient psychiatry or OCIC. TS will be measured once with the Client Satisfaction Questionnaire (CSQ-8) 95 after completion of telehealth, OCIC or inpatient treatment which is typically completed by week 3 (but could be completed by week 2 to week 6).
- COVID-19 Impact survey will be completed at week 2 and will gather information regarding the impact of the pandemic on the participant and families social, emotional, and economic functioning.

- The Self-Assessment Manikin (SAM) questionnaire will be completed at baseline and week 12 follow up survey.

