4.1. Overall Design

The study conceptual framework is illustrated in Figure 1. Briefly, we have proposed an observational design. Eligible individuals will be identified during a crisis assessment, either in the emergency department or during an emergency phone or telehealth assessment. Once the individual has been assessed and assigned to the clinician for treatment, study staff will assess if the patient is appropriate for the study using the study eligibility criteria. Individuals who receive treatment in one of the following treatment arms will be eligible for this observation study: inpatient, in-person OCIC or telehealth crisis intervention service. Eligible individuals will be contacted by study staff to introduce and offer the study. If patient and guardian agree, they will complete surveys at baseline and every 2 weeks for 6 months to evaluate outcomes.

Figure 1

Clinical features will be measured with the CHRT-SR, Suicidal Event Form for START, and our short START-Clinical Features (CF) form at baseline and every two weeks (see Schedule of Events) to evaluate HTE's. A one time survey will be completed at week 2 that collects information related to the impact of COVID-19 on the family. To decrease clinician, patient, and family burden, the scales are self-report short forms. All START follow up forms will be sent to participants and guardians every 2 weeks via email prompts in REDCap and data will be collected upon return from participants. Study CRCs will make best efforts to contact families for reminder to complete data within the study milestone window, however completion at each milestone marker is not ensured due to nature of population group. Data will be collected when available. The research coordinators, a research team member, or clinicians will ensure the

completion of the Suicidal Event Form for START and the brief START-CF form based on EHR review and/or other sources of information (family and patients) within 72 hours of admission (baseline) to inpatient, telehealth CIS, or OCIC and every two weeks. The research coordinators will search the EHR for all hospitals (with permission and consent) on weekly basis for suicidal events which may have ICD-10-CM code.¹⁰⁰ We developed this plan based on feedback from patients, families, and clinicians.

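### Section 7.2 records an unreachable participant as withdrawn, so with Section 6.2 follow-up for the primary event can end through silence alone, although the weekly EHR search needs no contact

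*Combined protocol and SAP*

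**What the plan says.** - **Section 7.2 (Lost to Follow Up).** A participant is lost to follow-up who "repeatedly fails to complete surveys and/or fails to return for scheduled visits and is unable to be contacted by the study site". The site must first try to regain contact ("where possible, 3 telephone calls and, if necessary, a certified letter"). If that fails: "Should the participant continue to be unreachable, he/she will be considered to have withdrawn from the study with a primary reason of lost to follow-up".
- **Section 8.** One missed survey has no such consequence: "that window will be skipped and study team will request data at the next milestone window".
- **Section 6.2 (Treatment Compliance).** This rule covers a different trigger and begins "For patients who are not treatment compliant, attempts will be" made to encourage treatment, with up to two calls or texts. If these patients cannot be contacted or refuse treatment, "we will continue to follow them until they withdraw from the study".
- **Section 4.1 (Overall Design).** "The research coordinators will search the EHR for all hospitals (with permission and consent) on weekly basis for suicidal events". The suicidal event form may be completed from EHR review or from family and patients.
- **Section 7.1.** Withdrawal of consent is a separate case: "If the participant withdraws consent for disclosure of future information, the sponsor may retain and continue to use any data collected before" that withdrawal.
- **Section 8.2.1.** AEs and SAEs are collected to the 180-day follow-up or until the participant completes the milestones.
- **Section 9.2.** Handling of missing data is left to an analysis plan to be finalised before database lock.

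**The concern.** The primary outcome is time to first recurrence of a suicidal event, analysed with a Cox model. Section 2.2 defines the event as an attempt, an interrupted attempt, a hospitalization or an emergency evaluation for suicidal risk, or death by suicide. Several of these leave a hospital record whether or not the family answers a survey. A label of withdrawn invites a coordinator to stop looking, and an analyst to censor at the last survey.

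Cox regression assumes that a censored participant has the same later risk as comparable participants still under observation. The protocol gives a reason to doubt this for disengaged patients: SA4 hypothesizes that the no-show group will have earlier and more suicidal events. Section 6.2 is the rule meant to keep that group under observation, and any of them who become unreachable also meet Section 7.2. The primary comparison, SAE surveillance and SA4 are all exposed. Deferring missing-data rules to a later analysis plan does not cure this, because an analysis cannot recover events that nobody searched for.

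**Working it through.** **1. The rules side by side**

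| Question | Section 6.2 | Section 7.2 | Section 4.1 |
|---|---|---|---|
| Who | Treatment non-compliant, unreachable or refusing | Repeated survey or visit non-response, unreachable | All participants, subject to permission and consent |
| What happens | Followed until withdrawal | Deemed withdrawn | Weekly EHR search |
| Needs contact? | Not stated | Triggered by lack of contact | No |
| End of follow-up | Withdrawal | The label is withdrawal | Not stated |

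For an unreachable no-show, Section 6.2 runs until withdrawal and Section 7.2 makes being unreachable count as withdrawal. Section 6.2 then has little effect for the group it addresses. No section says whether the EHR search survives the label or what the censoring date is.

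**2. The plan's own figure**

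Inputs (Section 9.1): 244 recruited, 10% dropout, 220 completers.
244 × (1 − 0.10) = 219.6, or 220. The figure reproduces.
Number exposed: 244 × 0.10 = 24.4, about 24. This is an upper figure, since some dropout will be withdrawal by request.

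**3. Patients with an event among those exposed**

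Input (Section 2.2): 27.3% of Dallas respondents reported a suicidal event within six months.
- All participants: 244 × 0.273 = 66.6, about 67.
- Exposed, average risk, lost at day 0, no EHR capture afterwards: 24.4 × 0.273 = 6.7, about 7.
- Same, but with twice the average risk (an assumption): 24.4 × 0.546 = 13.3, about 13.
- Average risk, loss spread evenly over six months, constant hazard (assumptions): λ = −ln(1 − 0.273) = 0.319. The mean chance of a first event after loss is 0.273/0.319 − 0.727 = 0.129, and 24.4 × 0.129 = 3.1, about 3.
- EHR search continues in practice: fewer still.

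**4. Sensitivity of the comparison, using the Section 9.1 planning rates**

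Inputs: 75 OCIC and 70 inpatient completers; six-month rates of 10% and 19%. These rates are for attempts and readmission respectively, so they are narrower than the composite event. A 10% loss in each arm is assumed.

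| | OCIC | Inpatient |
|---|---|---|
| Recruited | 75/0.9 = 83.3 | 70/0.9 = 77.8 |
| Lost | 8.3 | 7.8 |
| Events in completers | 75 × 0.10 = 7.5 | 70 × 0.19 = 13.3 |
| Risk if no lost participant had an event | 7.5/83.3 = 9.0% | 13.3/77.8 = 17.1% |
| Risk if every lost participant had an event | 15.8/83.3 = 19.0% | 21.1/77.8 = 27.1% |
| Risk if the lost have twice the arm's rate | (7.5 + 1.67)/83.3 = 11.0% | (13.3 + 2.96)/77.8 = 20.9% |

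Expected losses in the OCIC arm (8.3) exceed its expected events (7.5). The bounds are extreme, but they show that with so few events the handling of lost participants can move the comparison.

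**The case against.** Four stronger readings are tempting, and the documents do not support them.

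- **That the plan stops follow-up.** Section 7.2 does not end the EHR search, which is conditioned on permission and consent rather than on survey response. Section 8.2.1 runs AE and SAE collection to day 180 with no stop at loss of contact. What remains is silence on whether the search continues, next to a label that suggests it does not.
- **That Sections 6.2 and 7.2 contradict each other.** They have different triggers and contact efforts and can be read in sequence. The sequence still ends in withdrawal, so they are circular rather than opposed.
- **That a patient is censored before the event behind the silence is looked for.** If repeated failure means at least two missed two-weekly surveys, about 2 × 2 = 4 weeks pass first, hence about four weekly searches, and then the contact attempts. A hospital event that caused the silence would normally have been looked for by then. Guardians also receive the forms, and nothing shows why families go silent. Mainly later events are exposed.
- **That telehealth will look falsely safe.** Survey prompts go out by email in every arm, and treatment contact is brief everywhere against 180 days (inpatient stays of 6 to 8 days, for example). Differential loss is possible, but its direction is not shown.

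Two further objections stand in part. Dallas non-response at six months was 78 of 364 (21.4%), but that is one follow-up contact, not loss after this plan's contact procedure, so it is not used for the size here. EHR review also misses some events, which limits the remedy without removing the case for it.

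**Conclusion.** The point holds as a defect in a stated rule. Section 7.2 treats loss of contact as withdrawal, and with Section 6.2 this lets silence alone end follow-up for the primary event while a consented source that needs no contact is available. The consequence is a risk of informative censoring and a weaker SA4. It is not a demonstrated bias, and no direction between arms can be claimed.

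The size is up to about 24 of 244 participants, and about 7 patients with an event as a ceiling at average risk. That ceiling assumes that all dropout falls under Section 7.2, that loss occurs at day 0, that nothing is captured from the EHR afterwards, and that the Dallas respondents' six-month rate applies. Loss spread over follow-up gives about 3; twice the average risk would raise the ceiling to about 13. The documents give no event risk for lost participants. Sections 4.2 and 9.2.3 also describe the Cox comparison over three months, for which the counts would be smaller.

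**What to change.** - **Section 7.2:** record these participants as *discontinued surveys (lost to contact)* instead of withdrawn.
- **Sections 7.2 and 4.1:** state that the weekly EHR search, and EHR-based collection of suicidal events and SAEs, continue to day 180, consistent with Section 8.2.1. They stop if the participant or guardian withdraws from the study or withdraws consent, and stay within the scope of the consent given. The consent pages are not available here, so that scope must be checked.
- **Section 6.2:** reconcile with this, so that failed contact does not count as withdrawal.
- **Analysis plan:** in the Cox model, count EHR-detected events and censor at the last EHR search. Add a sensitivity analysis that censors at the last survey contact, and report the number lost to contact by arm.

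The cost is a few sentences and continued use of a search already planned. The drawback is incomplete ascertainment: interrupted attempts, and attempts never brought to care, may not appear in the EHR. Time covered by the EHR alone should therefore not be described as fully observed; the sensitivity analysis shows how much the result depends on it.
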